**Can Refinements to Effective Transitional Care Services Improve Outcomes? Results
from a Pragmatic, Randomized Controlled Trial**

Study Protocol and Statistical Analysis Plan

NCT03353155

November 22, 2017

Study Protocol and Statistical Analysis Plan

November 22, 2017

Objectives

The National University Hospital System is piloting a new care coordination program named CareHub. We aim to evaluate the effect of CareHub (compared to usual care) on resource utilization (using hospital administrative records), as well as patient and caregiver quality of life (using survey data).

CareHub includes the streamlining of post-discharge care, providing more structured and regular telephone support and checks, having a call center where tele-consultation will be available, early identification and preparation for post-discharge care by a multi-disciplinary team. We hypothesize that CareHub will improve outcomes of patients at high risk of readmission.

Background

NUHS has a variety of transitional / post-discharge care programs into which patients may be enrolled. Each of these programs is run by a different hospital team, so a patient may have to liaise with many parties for their post-discharge care. NUHS is currently piloting an improved post-discharge care program called CareHub. The pilot will run from 20 April 2016 – May / June 2017. CareHub is designed to streamline post-discharge care and better coordinate current programs for patients at high risk of readmission. The novel features of CareHub are (a) Provision of a single point of contact for all the patient's needs, to help patients and their families navigate the healthcare system as well as various programs available in the hospital and community. CareHub staff identify patients and start working with the care team during the inpatient phase, and will follow the patient through to the post-discharge phase (b) More structured and regular telephone support and checks, to help ease the hospital-to-home transition, as well as to provide more opportunity to verify that patients are adhering to their recommended treatment (c) A call center which will operate during office hours, where tele-consult will be available from CareHub staff (d) A consolidated multi-disciplinary discharge plan, based on the input of all healthcare workers caring for the patient. These include CareHub staff, ward doctor and nurse, heart failure care manager, and allied health professionals, as required (e) Early identification and preparation for post-discharge care. Healthcare workers listed in (f) will participate in a daily in-patient multi-disciplinary ward huddle, to discuss the patient's condition and start early preparation for post-discharge care. The two main features of CareHub that are likely to improve patient outcomes are structured telephone support (STS) and care coordination. Recent systematic reviews of randomized trials found that tele-monitoring / STS reduced hospital readmission rates and improved patients' health-related quality of life (Kronick et al. 2014; Louis et al. 2003; Inglis et al. 2015; Clark et al. 2007). However, the variation in effectiveness was large, perhaps due to differences in institutional context and implementation between studies. In addition, while STS appears to be cost effective, few studies in the literature have carried out cost-effectiveness analyses using prospectively collected data. Compared to tele-monitoring

and STS, fewer randomized trials have studied the effect of care coordination on post-discharge outcomes of cardiac patients. These studies found conflicting results on the effectiveness of care coordination, in part due to variation in institutional context as well as the types of intervention provided (Peikes et al, 2009; Harrison et al.,2002; Naylor et al, 2004). In all, the available evidence suggests that the two main features of CareHub are likely to result in positive changes to patient outcomes as well as reductions in resource utilisation.

Design

Inclusion and Exclusion Criteria and Consenting

The sample will include all cardiac patients who are eligible for CareHub, and were admitted to Wards 63 / 64 (post-cardiac surgery recovery wards) at NUH during the CareHub pilot. Recruitment for this pilot will be from 20 April 2016 – end November 2016, and the CareHub team will provide 6 months of post-discharge support.

All patients meeting a pre-defined minimum LACE score will be enrolled into the program and randomly assigned to CareHub or Usual Care (the existing package of post-discharge care services). All patients between 18 and 99 years of age will be included. Patients below 18 years of age will be excluded. Patients that do not consent or are unable to consent to the program will be excluded.

We will aim for a balanced design, as far as possible, in which the number of patients in the Usual Care and CareHub groups will be equal.

Written informed consent will be sought from patients admitted to Wards 63 /64 by a ward nurse that is not part of the study team. Request for informed consent will be delivered in the primary language of the patient (English, Mandarin Chinese or dialect, Malay or Tamil).

Individuals who agree to participate in the survey will be eligible for a lottery consisting of 10 prizes of \$10 each. The lottery will take place in May 2017. Winners will be informed by phone and the prize will be mailed to them. The lottery is meant as partial compensation for participants' time spent answering the survey. We choose the lottery, rather than a guaranteed sum due to budget constraints. The amount of the lottery is set at the low amount of \$10 to avoid undue influence of patients' decisions regarding survey participation.

Sample size

NUHS estimates that the total size of the population during the 6 month period to be approximately 1000 patients, of which 250 will be enrolled in CareHub, with a corresponding 250 in the control group. For the survey, due to resource constraints, we aim to randomly survey a total of 400 pairs of patients and their caregivers. 200 from CareHub and the rest from the control group.

The control group is anticipated to be a robust control because NUH randomly allocates the pool of eligible patients into CareHub and existing care. Table 1 summarizes the minimum detectable standardized effect size (MDE) for outcomes measured by the survey based on a 5% (2-sided) Type 1 error rate, different survey response rates, and different levels of statistical power for survey respondents. The MDE for outcomes captured by hospital administrative data will be lower (i.e. better) than those in the 100% response column, because administrative data are available for a larger group of patients.

Table 1

Total no. of patients in the CareHub and non- CareHub groups responding to the survey (response rate)	400 (100%)	300 (75%)	200 (50%)	120 (30%)
	Minimum detectable effect sizes			
80% power	0.28	0.32	0.40	0.52
90% power	0.32	0.38	0.46	0.60

Assumptions: (i) Survey response rates from the treatment and control groups are the same
(ii) Outcome variable is a continuous variable

Methods

Data

De-identified data will be extracted from the administrative and patient records. We will verify part of the administrative data, such as readmission rates, with a national database maintained by the Ministry of Health, that includes reportable readmissions data. We will also conduct a short survey to gauge patient and patient family satisfaction as another outcome measure.

We will use deidentified patient-related data from administrative databases of all public health institutions (PHIs) over the period Oct 2015 – Jun 2017. We sought and have obtained a waiver of informed consent for retrospective use of patients' administrative data. Our use of deidentified patient-related data from administrative databases from PHIs other than NUH has been approved by the Ministry of Health (MOH). We will collect additional data from patients and caregivers using surveys that we plan to carry out over the phone just after discharge, as well as one, two and six months after discharge. Each survey should take around 15 minutes. Consent for the follow surveys will be obtained as discharge.

Data on patients' compliance behaviors will be obtained during their scheduled specialty outpatient clinic visits, including a pill count, and clinical indicators such as HbA1C, fasting lipids, blood pressure, height, weight, ambulatory status.

Outcome measures

Our primary measures are length of stay at readmission, number of readmissions within 90 days, number of visits to the specialty outpatients clinics, the number of emergency department visits (planned and unplanned) post-discharge, and patient satisfaction.

Statistical Analysis Plan

Inpatient and discharge data will come from the National University Hospital, Singapore. Other data on health service utilization outside the NUH system will come from the Ministry of Health omnibus dataset.

We will compare the outcome variables between the control (non-CareHub) and treatment (CareHub) groups using t-tests, Chi-square tests and hazard models depending on the variable type.

We will also control for any differences in baseline characteristics of patients (e.g. in comorbidities and types of healthcare interventions received) and caregivers in the control and treatment groups by regression analyses. We acknowledge that we will face the multiple comparisons problem (i.e. as more outcomes are considered, it becomes increasingly likely that the control and treatment groups will differ on at least one outcome by random chance alone) by examining such many outcome variables.

We will consider the following methods to counteract the problem of multiple corrections: Bonferroni correction; comparing the number of outcomes with significant differences to the total number of outcomes examined; creating an index that combines certain outcome variables.

We will also be performing a cost-effectiveness analysis that compares the relationship between difference in costs and selected outcomes across the treatment and control groups. Examples of outcomes include number of readmissions or unplanned readmissions and quality adjusted life years.

All statistical analyses will be performed with Stata 13.0.

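### Non-response to the phone surveys is planned for only as lost precision; the planned baseline regression does not cover response that depends on post-discharge events differently by arm

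*Combined protocol and SAP*

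**What the plan says.** Outcome measures lists patient satisfaction among five primary measures. Under Methods, Data, satisfaction is gauged by survey, and the surveys are done by phone soon after discharge and again at one, two and six months.

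Under Sample size, "we aim to randomly survey a total of 400 pairs of patients and their caregivers", split as "200 from CareHub and the rest from the control group". Table 1 gives minimum detectable effects "based on a 5% (2-sided) Type 1 error rate", with "different survey response rates, and different levels of statistical power for survey respondents". Its columns are 400 (100%), 300 (75%), 200 (50%) and 120 (30%) responders. It lists two assumptions: a continuous outcome, and "Survey response rates from the treatment and control groups are the same". Only the second concerns non-response.

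The Statistical Analysis Plan section says: "We will compare the outcome variables between the control (non-CareHub) and treatment (CareHub) groups using t-tests, Chi-square tests and hazard models", chosen by variable type. It adds regression to control for baseline differences in patients and caregivers. It names no weighting, imputation, comparison of responders with non-responders, or sensitivity analysis for missing survey answers.

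For hospital records, Sample size says that "administrative data are available for a larger group of patients", and Methods, Data says: "We sought and have obtained a waiver of informed consent for retrospective use" of those records.

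**The concern.** Equal response rates are enough for Table 1, which concerns precision. They do not make the responders in the two arms alike. Randomisation protects the comparison of the patients sampled, not of the subset who pick up the phone.

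This design gives a specific reason for worry. The Background section describes CareHub as adding phone checks, a single contact point and a call center. The Design section gives six months of such support, and the surveys use the same channel over the same six months. A readmitted or struggling patient may stay easier to reach in the CareHub arm than under usual care. If readmission also lowers satisfaction, the responder difference moves away from zero with no true effect, and the nominal 5% test for a primary measure is no longer a 5% test.

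The planned regression uses baseline characteristics. Readmissions and emergency visits happen later, so that model does not see them. The hospital records do, and they reach beyond the people who answer the survey.

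**Working it through.** **1. Table 1 is a pure precision calculation.** Inputs from Sample size: two-sided 5%, power 80% or 90%, equal arms, standardised outcome. Formula: MDE = (1.960 + z_power) × √(2/n per arm), with z = 0.842 or 1.282.

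| Responders | n per arm | √(2/n) | 80%: 2.802 × √(2/n) | Stated | 90%: 3.242 × √(2/n) | Stated |
|---|---|---|---|---|---|---|
| 400 | 200 | 0.1000 | 0.280 | 0.28 | 0.324 | 0.32 |
| 300 | 150 | 0.1155 | 0.323 | 0.32 | 0.374 | 0.38 |
| 200 | 100 | 0.1414 | 0.396 | 0.40 | 0.458 | 0.46 |
| 120 | 60 | 0.1826 | 0.512 | 0.52 | 0.592 | 0.60 |

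All eight entries reproduce to within 0.01, and power at the stated values is 79.1% to 81.3% and 89.3% to 90.8%. Response rate enters only through n.

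**2. When baseline regression is enough.** In a simulation with 200 sampled per arm, no true effect, and response driven by a measured baseline variable in one arm only, the responder t-test was biased by 0.07 to 0.29 SD. Regression on that variable among responders brought the bias to 0.005 or less, and response weighting to 0.012 or less. In this case non-responder records add nothing essential.

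**3. When it is not enough.** None of the following inputs is in the documents; all are assumed. About 30% of patients are readmitted in each arm. Readmission lowers satisfaction by g = 0.5 or 1.0. A baseline variable has slope −0.2 on satisfaction and also raises readmission risk. Residual SD is 0.95. CareHub patients respond at one rate regardless of readmission; usual-care patients respond less often after readmission. There is no true effect. Ignoring a small covariance, outcome variance is 0.95² + 0.2² + g² × 0.3 × 0.7 = 0.995 or 1.153, so the SD is about 1.0 to 1.1 and results can be read roughly as SDs.

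The direct part can be done by hand. With usual-care response 0.60 if not readmitted and 0.25 if readmitted:
- overall usual-care response = 0.7 × 0.60 + 0.3 × 0.25 = 0.495, against 0.50 in CareHub;
- readmitted share of usual-care responders = 0.075 / 0.495 = 0.152, against 0.300 in CareHub;
- bias = g × (0.300 − 0.152) = 0.074 or 0.148.

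The same steps with 0.85 and 0.50 (CareHub 0.75) give overall response 0.745, share 0.201 and bias 0.049 or 0.099. With 0.38 and 0.12 (CareHub 0.30) they give 0.302, 0.119 and 0.090 or 0.181.

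Simulation of the full scenario (4,000 runs per setting), absolute bias and rejection rate for g = 0.5 to 1.0:

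| Response | Responder t-test | Baseline regression | Weighting by arm and readmission |
|---|---|---|---|
| 75% | 0.060 to 0.104; 8.8% to 12.6% | 0.048 to 0.091; 7.4% to 11.2% | ≤ 0.006; 4.6% to 5.3% |
| 50% | 0.089 to 0.164; 10.4% to 19.2% | 0.072 to 0.143; 8.8% to 16.4% | ≤ 0.001; 4.1% to 4.7% |
| 30% | 0.108 to 0.207; 9.4% to 18.7% | 0.087 to 0.182; 7.8% to 16.6% | ≤ 0.004; 3.4% to 4.8% |

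Regression removes the part that runs through the baseline variable and leaves roughly the hand-calculated part. In this scenario CareHub looks worse than it is; other response patterns could reverse the sign.

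**4. Scale.** The bias left by regression, against Table 1's 80%-power MDE, runs from 0.048/0.32 = 15% to 0.143/0.40 = 36%.

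**The case against.** The best defence is the regression. A reader might infer from the list of tests that responders are compared with no adjustment at all. The documents do not support that: regression on baseline characteristics is planned, and step 2 shows that it deals with response driven by measured baseline variables. What it leaves open is response driven by later events.

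Other stronger readings also fail:
- **That usual-care patients have no phone contact.** Usual care is the existing package of services, and whether it includes calls is not stated. CareHub is described as offering more, so the contrast is one of degree.
- **That 30% response is expected.** It is the lowest of four scenarios.
- **That hospital records on every patient would cure the problem.** The text says only that "administrative data are available for a larger group of patients". Full coverage of those randomised is a reasonable inference, not a statement. The records can reduce only the part of the bias that recorded variables predict.
- **That the records are ready to use for this.** They are described as de-identified, and linkage to survey answers is not described. The planned regression of outcomes on comorbidities suggests that a link exists.

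Two limits also stand. Post-discharge events cannot explain response to the survey done soon after discharge, so this mechanism concerns the later waves. Satisfaction is undefined for patients who have died by a given wave.

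**Conclusion.** The point holds in this form: for a primary measure collected by phone, non-response is planned for only as lost precision, and nothing beyond baseline regression addresses who responds. Table 1 itself is sound as a precision table. If response depends on post-discharge events in the same way in both arms, with equal rates and no true effect, there is no bias. If it depends on them differently, baseline regression leaves most of it: 0.05 to 0.18 in the illustration, with false rejection of 7.4% to 16.6% against a nominal 5%.

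Those figures rest entirely on the assumed readmission effect and response pattern. The documents give no response data, so the true size is unknown and could be negligible. It would be going too far to say that the satisfaction result will be biased. The conclusion is that a cheap, better analysis is available and should be specified.

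**What to change.** In the Statistical Analysis Plan section:
- Make the main analysis of satisfaction and other survey outcomes use all patients sampled for the survey and alive at the wave. Use inverse-probability-of-response weights or multiple imputation, fitted separately by arm.
- Name the predictors: LACE score, age, index stay and prior utilisation. For the one-, two- and six-month waves, add readmissions and emergency visits up to that wave. These belong in the response or imputation model. Adding them as covariates to the outcome regression would condition on events after randomisation.
- Keep the responder-only test and the baseline-adjusted regression as sensitivity analyses.
- Add a sensitivity analysis for response that depends on satisfaction itself, which the records cannot correct.
- Tabulate response, and the administrative profile of responders and non-responders, by arm and wave.
- State that survey and administrative records share a study key.

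Under Table 1, note that equal rates are assumed for precision only.

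The cost is plan wording and modest analysis work on data already to be extracted, with no new patient contact. Intervals may widen slightly, more so at low response, and only bias predicted by recorded variables is reduced. If no study key exists, the weighting or imputation cannot be done as described.

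### As worded, the primary measure of length of stay at readmission exists only for readmitted patients, so randomisation does not protect the comparison and the general MDE statement does not cover it

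*Combined protocol and SAP*

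**What the plan says.** Outcome measures lists five primary measures, beginning: "Our primary measures are length of stay at readmission, number of readmissions within 90 days, number of visits to the specialty outpatients clinics". The 90-day window is attached only to the number of readmissions. For stay length the plan gives no analysis set, no value for patients never readmitted, no time window and no rule for patients with several readmissions.

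The Statistical Analysis Plan section says: "We will compare the outcome variables between the control (non-CareHub) and treatment (CareHub) groups using t-tests, Chi-square tests and hazard models". The choice among these follows the type of variable, and regression adjusts for baseline differences. Neither is described as dealing with selection into readmission.

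Background cites reviews that "found that tele-monitoring / STS reduced hospital readmission rates" and concludes that CareHub is likely to reduce resource use.

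Sample size plans 250 patients per arm, of whom 200 per arm are surveyed. Table 1 gives MDEs for the survey outcomes "based on a 5% (2-sided) Type 1 error rate". The text then adds: "The MDE for outcomes captured by hospital administrative data will be lower (i.e. better) than those in the 100% response column". The reason offered is that more than the 400 surveyed patients contribute such data. No exception is made for an outcome that exists only in some patients.

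**The concern.** Random allocation makes the two groups of 250 comparable. It does not make the readmitted patients in one group comparable with the readmitted patients in the other, because who is readmitted may depend on the arm. If CareHub mainly prevents short, avoidable readmissions, those that remain are the longer ones and mean stay goes up. If it mainly prevents long ones, mean stay goes down. If it prevents both in proportion, mean stay does not move. A t-test or hazard model on the readmitted does not remove this selection, and adjustment for measured baseline variables does not by itself restore comparability.

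One of five primary results could therefore appear to show harm, or no effect, under an intervention that reduces hospital use. The documents do not show which direction applies.

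The second issue is precision. The MDE statement rests on more than 400 patients contributing data, and for stay length only the readmitted contribute.

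**Working it through.** **Inputs from the documents.** 250 per arm in total; 200 per arm surveyed; two-sided 5%; Table 1 MDEs for 400 patients of 0.28 (80% power) and 0.32 (90% power).

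**Inputs that are assumed.** The documents give no readmission rate and no distribution of stay length. Everything below that uses either is illustrative.

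**Step 1: reproduce Table 1.** MDE in SD units = (z for two-sided alpha + z for power) × √(2 / n per arm).
- 80% power, n = 200: (1.960 + 0.842) × √(2/200) = 2.802 × 0.100 = 0.280. Table 1 says 0.28.
- 90% power, n = 200: (1.960 + 1.282) × 0.100 = 0.324. Table 1 says 0.32.
- The other six cells also reproduce; power at each stated MDE is within 2 points of nominal.

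**Step 2: all 500 patients.** n = 250: 2.802 × √(2/250) = 0.251 at 80% power and 3.242 × 0.0894 = 0.290 at 90%. The MDE statement is correct for outcomes defined in every randomised patient.

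**Step 3: readmitted patients only.** With readmission proportion r, taken as equal in both arms, and one value per readmitted patient, n per arm = 250r. MDE at 80% power:

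| Assumed r | n per arm | Normal formula | Noncentral t |
|---|---|---|---|
| 20% | 50 | 0.560 | 0.566 |
| 30% | 75 | 0.457 | 0.460 |
| 50% | 125 | 0.354 | 0.356 |
| 80% | 200 | 0.280 | 0.281 |

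The statement holds for this measure only if more than 400/500 = 80% are readmitted.

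**Step 4: direction of the comparison.** Assume 30% of controls are readmitted once, 60% of those stays lasting 3 days and 40% lasting 12. So 18% of controls have a short stay and 12% a long one.
- Control: bed-days per patient = 0.18 × 3 + 0.12 × 12 = 1.98; mean stay = 1.98 / 0.30 = 6.6.
- A, one third of short stays prevented: bed-days = 0.12 × 3 + 0.12 × 12 = 1.80 (−9%); mean stay = 1.80 / 0.24 = 7.5 (+14%).
- B, one third of long stays prevented: bed-days = 0.18 × 3 + 0.08 × 12 = 1.50 (−24%); mean stay = 1.50 / 0.26 = 5.8 (−13%).
- C, one third of both prevented: bed-days = 0.12 × 3 + 0.08 × 12 = 1.32 (−33%); mean stay = 1.32 / 0.20 = 6.6 (unchanged).

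**Step 5: how often a test would be significant.** 20,000 simulated trials per pattern, 250 per arm, pooled t-test at 5%:

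| Pattern | Stay among readmitted | Bed-days per randomised patient |
|---|---|---|
| A | 21% (almost all longer under CareHub) | 8% |
| B | 20% (almost all shorter) | 32% |
| C | 5% (chance level) | 54% |
| No effect | 5% | 5% |

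**Step 6: scale of the per-patient measure.** Control variance = 0.18 × 9 + 0.12 × 144 − 1.98² = 14.98, so SD = 3.87 days. An MDE of 0.251 SD is 0.251 × 3.87 = 0.97 days, or 0.97 / 1.98 = 49% of the control mean.

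**The case against.** The strongest reply is that the plan does not settle the reading. The measure is named in a few words, and the claim that administrative outcomes draw on more patients fits authors who pictured everyone contributing, with zeros for those not readmitted. On that reading both the selection and the MDE points disappear. This is suggestive only: no section says it, and the plain wording points the other way.

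Second, readmissions within 90 days is also primary and is defined for everyone. In the same illustration a t-test on any readmission has about 32%, 17% and 74% power in A, B and C, which beats bed-days in A and C. That stands, and it limits the harm to the trial's overall message. It does not repair this measure.

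Third, the frequencies depend on stays of exactly 3 or 12 days. Adding lognormal scatter (assumed log-SD 0.7, means unchanged) cuts the significant results on conditional stay to about 11% in A and 10% in B. Power for bed-days falls to roughly 6 to 7%, 21% and 35 to 37%. That stands too: the frequencies are illustrative. The mean shifts in Step 4 are unchanged.

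Fourth, replacing stay duration by total days changes the question, and does so late. The change of question is real, but the Objectives section sets resource utilisation as an aim, and total days addresses it directly. The timing is dealt with under the fix.

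**Conclusion.** The concern holds. Followed as written, the plan makes a primary comparison between subsets selected by an event that CareHub is expected to influence, and the listed methods do not correct for that. The direction and size of any bias cannot be determined from the documents; the example shows only that mean stay can move by +14%, −13% or 0% while bed-days fall by 9%, 24% or 33%.

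The arithmetic of Table 1 is right, and so is the MDE statement for outcomes seen in all 500 patients. Its scope is too wide: for stay among the readmitted, the MDE at 80% power is 0.57, 0.46 or 0.36 SD at assumed readmission rates of 20%, 30% or 50%.

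The conclusion rests on the plain reading of the measure, with no value for patients not readmitted. The MDE figures also assume one value per readmitted patient. The point should be fixed; it affects one of five primary measures and leaves the other utilisation measures and the cost analysis intact.

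**What to change.** **Change.**
- Define the primary measure as total inpatient days on readmission within 90 days of index discharge, summed over all readmissions, zero if none.
- Analyse it in all randomised patients by assigned arm, with robust or bootstrap standard errors.
- Keep stay length among the readmitted as descriptive only.
- State how deaths within 90 days are handled. Add days alive and out of hospital only if death dates are available.
- Limit the MDE sentence to outcomes defined in every randomised patient: 0.25 SD at 80% power and 0.29 SD at 90%, at an unadjusted 5%.
- If zeros were already intended, a sentence saying so, with the window and the rule for repeat readmissions, is enough.

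**Cost.** Mainly SAP wording and programming. The current measure already needs readmission stays. Recruitment was planned to "end November 2016, and the CareHub team will provide 6 months of post-discharge support", and the plan uses "deidentified patient-related data from administrative databases of all public health institutions (PHIs) over the period Oct 2015 – Jun 2017". Data to the end of June 2017 give a full 90 days for index discharges up to about 1 April 2017. The SAP says that utilisation outside NUH comes from a Ministry of Health dataset, but not whether this includes stay lengths or death dates; that needs checking.

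**Downsides.** The new variable is skewed with many zeros and its power is modest: in the illustration the detectable difference is about half the control mean. The document is dated 22 November 2017, after planned recruitment, the pilot and the data window had ended. The change must therefore be dated and declared, stating whether outcome data by arm had been seen.

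### Do the missing windows for four of the five primary measures leave the multiplicity correction without a usable count?

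*Combined protocol and SAP*

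**What the plan says.** The Outcome measures section gives the primary set as "Our primary measures are length of stay at readmission, number of readmissions within 90 days, number of visits to the specialty outpatients clinics", followed by "the number of emergency department visits (planned and unplanned) post-discharge, and patient satisfaction". The 90 days are attached to the readmission count. Length of stay and clinic visits have no stated window, emergency visits start at discharge but have no end, and satisfaction has no time point.

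Three other periods appear, none of them presented as an outcome window. Design gives six months of support from the CareHub team. Methods, Data gives administrative data "over the period Oct 2015 – Jun 2017" and phone "surveys that we plan to carry out over the phone just after discharge, as well as one, two and six months after discharge".

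The Statistical Analysis Plan section acknowledges that testing many outcomes makes a chance finding likely. It then says "We will consider the following methods to counteract the problem of multiple corrections: Bonferroni correction". The second remedy on its list is "comparing the number of outcomes with significant differences to the total number of outcomes examined", and the third is "creating an index that combines certain outcome variables". It does not choose among the three, list the family, or name the components of an index. Table 1 under Sample size is "based on a 5% (2-sided) Type 1 error rate", with no correction, and covers survey outcomes only.

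**The concern.** Each remedy seems to need a settled list. Bonferroni needs a divisor, the tally needs a denominator, and an index needs one value per component. If satisfaction were tested at every survey and the three open utilisation measures were each tested over several windows, the five named measures would become 8, 11 or 14 variables. Dividing by five while reporting fourteen would let familywise error pass 5%. Dividing by fourteen would cost power. The window for length of stay also decides which patients enter that comparison, because only readmitted patients have a value.

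The document is dated 22 November 2017, after the data period ends in June 2017. A reader could therefore ask whether the definitions were still open when results by arm could be seen.

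**Working it through.** **1. Reproduce Table 1.** Inputs: 400 respondents, 200 per arm, two-sided 5%, SD 1. The minimum detectable effect is (z for alpha + z for power) × √(2/n per arm). At 80% power this is (1.960 + 0.842) × √(2/200) = 0.280, against the stated 0.28. Across the row it gives 0.280, 0.324, 0.396, 0.512 (stated 0.28, 0.32, 0.40, 0.52). The 90% row gives 0.324, 0.374, 0.458, 0.592 (stated 0.32, 0.38, 0.46, 0.60). The table is sound at an uncorrected 5%.

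**2. Possible counts.** Readmissions 1, plus three open utilisation measures at k windows, plus satisfaction at four surveys: 1 + 3k + 4 = 8, 11 or 14 for k = 1, 2 or 3. With one definition per measure the count is 5. The larger counts are assumptions. No passage proposes several windows for one measure. Methods, Data speaks of a short satisfaction survey without saying that satisfaction is asked at all four calls, so even 8 is an assumption.

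**3. Effect on power if every definition is counted** (200 per arm, 80% power; power at 0.28 is Φ(2.80 − z)):

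| Tests | Alpha per test | z | Detectable effect | Power at 0.28 |
|---|---|---|---|---|
| 1 | 0.05 | 1.960 | 0.280 | 80% |
| 5 | 0.01 | 2.576 | 0.342 | 59% |
| 8 | 0.00625 | 2.734 | 0.358 | 53% |
| 14 | 0.00357 | 2.914 | 0.376 | 45% |

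The fall from 80% to 59% is the price of Bonferroni over five measures, and it is paid even with every window fixed. The open definitions account only for the further step, from 0.342 to 0.358 or 0.376. For administrative outcomes at 250 per arm the corresponding figures are 0.306, 0.320 and 0.336.

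**4. Familywise error at 0.01 per test.** With one definition per measure, the Bonferroni bound is 5 × 0.01 = 5%, whatever definitions are taken and however they correlate. If 8, 11 or 14 independent tests were all counted at 0.01, the error would be 1 − 0.99^8 = 7.7%, 1 − 0.99^11 = 10.5% or 1 − 0.99^14 = 13.1%.

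Null simulations allowed for overlap between definitions. They used gamma-Poisson counts with 250 per arm, follow-up of 212 to 436 days, normal satisfaction scores with 200 per arm, and Welch t-tests. They gave 3.9 to 5.2% with five definitions, 6.1 to 7.6% with eight, 8.0 to 9.2% with eleven and 8.7 to 10.7% with fourteen. Dividing by fourteen gave 3.1 to 4.2%. Monte Carlo error is about 0.5 to 1 point. Rates, dispersion and survey correlation are assumed, so the ranges are illustrative.

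**5. The tally remedy.** With independent tests at 0.05, the chance of two or more false positives is 1 − 0.95^m − m × 0.05 × 0.95^(m−1) = 2.3%, 5.7% and 15.3% for m = 5, 8 and 14. Simulation with overlapping definitions gave 15.8 to 18.7% at 14, so most of the rise is simply more tests. The remedy already sets the tally against the total: two of 5 is 40%, two of 14 is 14%. On that scale the expected share is about 5% at either count. The simulated chance of a share of 40% or more is 1.8 to 3.5% with five and 0.03 to 1.7% with fourteen. Overlap does show in a less extreme tally: three or more of 14 occurred in 6.9 to 8.8% of runs, against 3.0% if independent.

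**6. Follow-up.** From 20 April 2016 to 30 June 2017 is 436 days; from 30 November 2016 it is 212 days, less the index stay in each case. Windows of 90 and 182 days are both complete for anyone discharged by 30 December 2016. If all data were used instead, observation time would vary between patients, but random allocation keeps it from differing systematically by arm.

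**The case for a change.** The case for a change is that this plan raises multiplicity itself and then leaves the count open, when one short table would close it at no cost in data. Four of five measures without a window is correct on the text. Carrying the 90 days over to length of stay is a natural reading, but it is still an inference and leaves three measures open. The date of the document does not show whether arms had been compared. If definitions were picked after seeing results, the 5% bound in step 4 would fail, and the error could approach the figures for the larger counts.

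The omission stands, and so does the caution about timing. The stronger claim, that the remedies cannot be applied, does not: five measures are named and can be divided by. Nor would windows alone settle the count. The family is never listed, no remedy is chosen, index components are unnamed, emergency visits could be one outcome or two, and length of stay could be the first, mean or total stay.

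Length of stay also compares a group formed after randomisation. Assuming 0.1 readmissions a month and dispersion 1, the share readmitted is 1 − 1/(1 + 0.1 × days/30.4), about 23% at 90 days and 37% at 182 days. If CareHub changes readmission, no window restores comparability, so this limit is separate from the missing windows.

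**Conclusion.** The definitions are incomplete, but nothing in the plan as written leads to a wrong result. An analyst who takes one sensible definition per measure, from the 90 days or six months already in the documents and one survey or an average of them, has a five-test family with error held at 5%. The harm needs a further step that the documents do not describe: counting several definitions as results while dividing by five, or choosing among them by their results. Then the error would be roughly 6% to 11%, under assumed event rates. If the count is honestly enlarged instead, the cost is 0.016 to 0.034 in detectable effect at 200 per arm (0.358 − 0.342 and 0.376 − 0.342). No definition favours an arm by construction, apart from the separate subset problem with length of stay. The point is a gap in documentation, and no change to the plan is called for.
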